#### Cavotricuspid Isthmus (Typical Atrial Flutter) Lesions

- After creating all left atrial lesions, sheaths may be removed from the left atrium and heparinization interrupted characteristic of no longer needing to maintain ACTs 300 to 400 seconds without instrumentation in the left atrium.
- Irrespective of inducibility, a cavotricuspid isthmus, right atrial typical flutter lesion should be created.
- Using standard endocardial ablation techniques, a segment of right atrium defining the cavotricuspid isthmus between the inferior vena cava and the tricuspid valve is ablated to interrupt a known pathway for typical atrial flutter.
- Bidirectional block should be confirmed across the isthmus lesion to ensure integrity of the connecting point ablations.

#### Post-Operative Management

- Drainage from the pericardial drain should be interrogated to monitor potential for bleeding or fluid build-up that could cause a pericardial effusion prior to removal. Recommendation from best practice symposiums is to leave the drain in place until drain output is less than a threshold of 50-100cc in a 24 hr period.
- A trans-thoracic echocardiography will be performed at 7+7 days post-operative to evaluate the patient for pericardial effusion.
- Recommendation from best practice symposiums is to administer a prophylactic regimen of steroids (and/or non-steriodals) to prevent Dressler's Syndrome, Pericarditis, and other inflammatory mechanisms that have been shown to cause late pericardial effusions, provided the patient is able to tolerate such regimen.
  - Example #1: 2 mg/ kg hydrocortisone immediately post-op; and 1 mg/kg of prednisone on Post-op day 1 and Post-op day 2.

[figure not shown]
## Convergent Epicardial and Endocardial Lesion Pattern

### Epicardial Lesions [blue]

- 1 Right Posterior Pulmonary Vein Lesions
- 2 Left Posterior Pulmonary Vein Lesions
- 3 Parallel Posterior Vertical Connecting Lesions
- 4 Right Anterior Pulmonary Vein Lesions
- 5 Left Anterior Pulmonary Vein Lesions

### Endocardial Lesions [red] (Located at Pericardial Reflections)

- 6 Right Superior Pulmonary Vein Lesions
- 7 Right Inferior Pulmonary Vein Lesions
- 8 Left Superior Pulmonary Vein Ridge Lesions
- 9 Cavotricuspid Isthmus (Typical Atrial Flutter) Lesions

**Attachment B**

**Control Arm Study Procedure**

Endocardial Catheter Ablation Procedure

---

### **Endocardial Catheter Ablation Procedure**

Preoperative requirements and patient preparation should follow the Investigator's and site's standard of practice for left-sided catheter ablation procedures.

Follow the suggested lesion creation steps described below. Access the anatomical locations endocardially, and create the lesion pattern which includes isolating the left and right pulmonary veins, connecting the PV isolation lesions with an atrial roof lesion, performing < 30 minutes of CFAE ablation if the rhythm does not convert into SR or organize into an AFL/AT, mapping and ablating AFLs/ATs induced, and ensuring bidirectional block across a cavotricuspid isthmus lesion. If additional lesion(s) are created or suggested lesions are not created, this must be entered into the electronic data capture system developed for the study.

#### **Endocardial Access**

- Using standard catheterization and sheath introduction techniques, access to the venous vasculature is obtained.
- A coronary sinus catheter is introduced to help monitor atrial electrograms, serve as a reference catheter for 3-D navigation, and provide electrodes from which pacing stimuli can be transmitted.
- For transeptal procedures, heparin needs to be administered to assure ACTs of 300 to 400 seconds to protect against thrombus formation while catheter instrumentation resides within the left atrium.
- Transeptal access is obtained prior to or after fully heparinizing the patient. Transeptal access is obtained by puncturing the fossa ovalis under ultrasound (ICE or TEE) guidance to provide access to the left atrium. Frequently, two transseptal sheaths may be utilized to facilitate insertion of an ablation catheter and diagnostic circular catheter into the left atrium. Alternatively, the ablation catheter may be inserted through the transeptal puncture site without the need for a sheath.

#### **Esophageal Temperature Monitoring**

Esophageal temperature monitoring should be utilized during endocardial ablation. At least one esophageal temperature probe should be positioned along the left atrium under fluoroscopic guidance. All other instrumentation including NG and OG tubes, and TEE probes need to be removed prior to placement of the esophageal temperature probe. Whenever possible, the position of the probe should be interrogated with fluoroscopy to ensure proximity to the ablation electrode. If esophageal temperature increases more than 0.5°C during lesion creation or above an absolute maximum of 38.0°C, RF energy should be terminated until the temperature reduces to baseline.

#### **Ablating Endocardial Tissue**

- Specific endocardial lesions will be created with an open irrigated-tip RF ablation catheter having unidirectional or bidirectional steering.
- Specific commercially available RF ablation systems that may be utilized during the study may include Therapy™ Cool Path™ family of Irrigated Ablation Catheter and associated accessories (St. Jude Medical, Inc.), Saffire BLU™ family of Ablation Catheter and associated accessories (St. Jude Medical, Inc.), or ThermoCool® family of Irrigated Tip Catheter and Integrated Ablation System (Biosense, Webster).
- 3-D navigation utilizing a Carto™ EP Navigation System (Carto 3 or Carto XP), or an EnSite™ System (NAVx™ or Velocity™) may be utilized to monitor the position of the ablation catheter electrode, facilitate endocardial mapping, and record ablation locations.

### **Endocardial Lesions**

The completion of each lesion described below may require multiple sequential placements. The suggested sequence of steps for lesion creation, are as follows:

#### **Left Pulmonary Vein Encircling Lesions**

- Using standard pulmonary vein isolation techniques, lesions encircling the left pulmonary veins should be created. A circular catheter may be utilized to guide creation of point lesions that interconnect into a series capable of interrupting propagation of electrical signals from the atrium to the pulmonary veins and vice versa.

#### **Right Pulmonary Vein Encircling Lesions**

- Using standard pulmonary vein isolation techniques, lesions encircling the right pulmonary veins should be created. A circular catheter may be utilized to guide creation of point lesions that interconnect into a series capable of interrupting propagation of electrical signals from the atrium to the pulmonary veins and vice versa.

#### **Anterior Left Atrial Roof Connecting Lesions**

- A left atrial roof lesion composing point ablations that connect the right and left pulmonary vein encircling lesions should be completed. This series of connecting point lesions should be interrogated to ensure completeness of the line capable of interrupting the propagation of electrical signals.

#### **Additional Endocardial Left Atrial Lesions**

- If the rhythm does not organize into an atrial tachycardia (AT) or atrial flutter (AFL), or convert to sinus rhythm after completing pulmonary vein isolation (PVI) and the roof lesion, then the electrophysiologist may spend up to 30 min performing CFAE ablation. The electrophysiologist may elect to convert the patient into sinus rhythm prior to endocardial mapping and ablation without performing CFAE ablation. CFAEs should be defined as constant activities or local activity with electrogram cycle length <120 msec.xii,xiii CFAE ablation must not involve creating linear lesions.
- If the patient still does not organize into an AT, AFL, or SR after CFAE ablation then the patient should be converted by administering Ibutilide or electrical cardioversion.

#### **Induced or Organized Atrial Arrhythmias**

- If atrial fibrillation organizes into an atrial arrhythmia (AFL, AT, AVNRT, etc.) or if an atrial arrhythmia is induced during Isoproterenol administration or rhythm challenging exercises, then mapping and localized endocardial ablation may be performed to target the specific atrial arrhythmia.

#### **Cavotricuspid Isthmus (Typical Atrial Flutter) Lesions**

- After creating all left atrial lesions, sheaths may be removed from the left atrium and heparinization interrupted characteristic of no longer needing to maintain ACTs of 300 to 400 seconds without instrumentation in the left atrium.

---

xii Knecht S, et al. Impact of pharmacological autonomic blockade on complex fractionated atrial electrograms. *J Cardiovasc Electrophysiol*. 2010;21(7):766-702.

xiii Oral H, et al. A randomized assessment of the incremental role of ablation of complex fractionated atrial electrograms after antral pulmonary vein isolation for long-lasting persistent atrial fibrillation. *J Am Coll Cardiol*. 2009;53:782-9.

[figure not shown]
---

- Irrespective of inducibility, a cavotricuspid isthmus, right atrial typical flutter lesion should be created.
- Using standard endocardial ablation techniques, a segment of right atrium defining the cavotricuspid isthmus between the inferior vena cava and the tricuspid valve is ablated to interrupt a known pathway for typical atrial flutter.
- Bidirectional block should be confirmed across the isthmus lesion to ensure integrity of the connecting point ablations.

## Endocardial Lesion Pattern

### Endocardial Lesions

- 1 Left Pulmonary Vein Encircling Lesions
- 2 Right Pulmonary Vein Encircling Lesions
- 3 Anterior Left Atrial Pulmonary Vein Roof Connecting Lesions
- 4 Cavotricuspid Isthmus (Typical Atrial Flutter) Lesions

**Attachment C**

**PV Conduction Block Confirmation Protocol**

---

**PV Conduction Block Confirmation Protocol**

**Testing Conduction block in the Pulmonary Veins (PVs)**

Procedure to test for conduction block must be performed and conduction block should be confirmed after the protocol required lesion pattern has been created. The pacing and / or electrogram recording equipment standard for the EP Lab at the site should be used to test for conduction exit or entrance block.

**To Test block:**

- Use an ablation device or diagnostic circular catheter to record electrograms from, and/or transmit pacing stimuli to the pulmonary vein antrum distal to the lesion, away from the left atrium.

**Exit Block Testing:**

- Ensure patient is in sinus rhythm. If patient is not in sinus rhythm, attempt to cardiovert the patient into sinus rhythm in order to pace
- Connect catheter pacing electrodes to EP stimulator
- Set pacing amplitude to  $\geq 10$  mA
- Ensure pacing rate is greater than the baseline heart rate
- Confirmation is achieved by not capturing heart rate despite transmitting pacing pulses to the PV antrum (for PVI).

**Entrance Block Testing**

- Patient may be in AF when testing entrance block
- Connect sensing electrodes of an ablation catheter or diagnostic circular catheter to an EP recording system
- Monitor cardiac electrograms from sensing electrodes in bipolar orientation
- Place sensing electrodes on PV antrum distal to the PV isolation lesion(s) for demonstrating PVI

Confirmation of Pulmonary Vein Isolation (PVI) is achieved by determining lack of electrogram signals on PVs, inability to capture when pacing the PVs, or dissociation of cardiac signals along PVs from resting heart demonstrating PV isolation.

**Attachment D**

**Anti-Arrhythmic Therapy Protocol**

---

**Anti-Arrhythmic Therapy Protocol**

The protocols for the use of class I or III AADs recommended in the 2012 HRS/EHRA/ECAS expert consensus statement and the ACC/AHA/ESC 2006 Guidelines for the Management of Patients with AF should be followed to manage the AAD therapy for subjects enrolled in both arms of the study.

Post procedure, subjects enrolled in both arms of the study should be prescribed class I or class III AADs the subject was taking prior to study enrollment or another failed class I or III AAD. Subjects who have a contraindication for class I or class III AADs should be followed as medically indicated.

All subjects should be weaned off their class I or III AAD at their 3 month post procedure follow-up visit unless the AADs are medically indicated or the subject is maintained on the same or lower dose of a previously failed class I or III AAD and the attending physician recommends continuation of such medical management prophylactically.

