### 1.3 Study Design

This is a, prospective, open label 2:1 randomized (convergent procedure versus standalone endocardial catheter ablation) multi-center pivotal clinical study. The study will enroll and randomize one hundred and fifty three (153) patients from up to thirty (30) sites, twenty-seven (27) US and three (3) OUS.

Potential subjects with symptomatic persistent AF will be screened by the sites for study participation. Consented subjects meeting all inclusion / exclusion criteria will be enrolled and randomized into the study.

Subjects in both arms of the study will be evaluated post procedure at 1 month, 3 months, 6 months and 12 months with a long-term follow-up visit at 18 months and long-term phone follow-up at 2, 3, 4, 5 years as detailed in this protocol. Submission for premarket approval will be filed after study subjects in both arms of the study complete the one year post procedure follow-up visit.

Annual reports will be submitted to the Agency in compliance with FDA regulatory requirements. One month safety data for the first 50 subjects in the treatment arm will be submitted to the FDA for review. During the conduct of this randomized study, any reported death, pericardial effusion leading to therapeutic drainage, atrio-aesophageal fistula or stroke will be reported to the Agency within 10 days.

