#### **1.5 Study Endpoints**

##### **1.5.1 Primary Efficacy Endpoints**

The primary efficacy endpoint is success or failure to be AF/AT/AFL free absent class I and III AADs except for a previously failed or intolerant class I or III AAD with no increase in dosage following the 3 month blanking period through the 12 months post procedure follow-up visit.

The results of the holter data used for the primary efficacy endpoint evaluation will be evaluated by an independent reviewer thus maintaining the objectivity of the primary efficacy endpoint.

Subjects will be considered primary efficacy failures if any of the following conditions are observed:

- Any electrocardiographically documented AF/AFL/AT episode of 30 sec duration or longer by Holter, event monitor or rhythm strip; or for the full 10 second recording of a standard 12 lead ECG following the 3 month blanking period through the 12 months post procedure follow-up visit.
- The use of a new or an increase in the dose of a previously failed class I or class III AAD following the 3 month blanking period through the 12 months post procedure follow-up visit.
- DC cardioversion for AF/AFL/AT following the 3 month blanking period through the 12 months post procedure follow-up visit.
- Subsequent left-sided catheter ablation for AF/AFL/AT at anytime during the 12 months post procedure follow-up visit.
- Catheter ablation for right-sided typical atrial flutter following the 3 month blanking period through the 12 months post procedure follow-up visit.

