2.3 Study Endpoints

2.3.1 Primary Efficacy Endpoints

The primary efficacy endpoint is success or failure to be AF/AT/AFL free absent class I and III AADs except for a previously failed or intolerant class I or III AAD with no increase in dosage following the 3 month blanking period through the 12 months post procedure follow-up visit.

Subjects will be considered primary efficacy failures if any of the following conditions are observed:

- Any electrocardiographically documented AF/AFL/AT episode of 30 sec duration or longer by Holter, event monitor or rhythm strip; or for the full 10 second recording of a standard 12 lead ECG following the 3 month blanking period through the 12 months post procedure follow-up visit.
- The use of a new or an increase in the dose of a previously failed class I or class III AAD following the 3 month blanking period through the 12 months post procedure follow-up visit.
- DC cardioversion for AF/AFL/AT following the 3 month blanking period through the 12 months post procedure follow-up visit.
- Subsequent left-sided catheter ablation for AF/AFL/AT at anytime during the 12 months post procedure follow-up visit.
- Catheter ablation for right-sided typical atrial flutter following the 3 month blanking period through the 12 months post procedure follow-up visit.

As described in Section 7.4.2, the blanking period is the period from index procedure through 3 months post-procedure visit.

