8.6 Non-Study Medications

All class I, II, III, and IV AADs, as well as other cardiac and anti-coagulants taken by the subject prior to and during study enrollment, will be recorded on the eCRF. All recorded non-study medications that are halted prior to the study procedure date will be classified as prior medications. Medications taken on or after the date of study procedure, including those taken both before and after the procedure, will be categorized concomitant. If insufficient information is available to definitively categorize a medication, it will be considered concomitant. No standardized classification of medications (such as using a drug dictionary) is currently planned.

All medications will be listed by subject. Prior medications will be indicated in the listing. Class I/III AADs will also be flagged in data listings, as well as presented in a separate listing. No summaries of medications will be presented.

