9.4 Secondary Efficacy Analysis

All secondary analyses will be performed on the ITT population. These analyses may be repeated on the mITT and PP populations.

9.4.1 $\geq 90\%$ Reduction in AF Burden

The AF burden, as a percentage, is recorded on the Holter Monitor eCRF. The recorded values and percent change from baseline in AF burden will be summarized by time point at 6, 12, and 18 months post-procedure.

The percent change from baseline at 12 months will be categorized as $\geq 90\%$ reduction (percent change $\leq -90\%$) or $< 90\%$ reduction (percent change $> -90\%$). The proportion of subjects achieving $\geq 90\%$ reduction at 12 months will be compared between treatment arms using Fisher's Exact test.

This analysis will be repeated for the following subsets of subjects:

- Subjects who have taken a Class I/III AAD during the efficacy evaluation period (excluding previously failed Class I/III AADs with no increase in dosage).

- Subjects who have *not* taken a Class I/III AAD during the efficacy evaluation period (excluding previously failed Class I/III AADs with no increase in dosage).
- Subjects who have taken any Class I/III AAD during the efficacy evaluation period.

No imputation will be performed for missing data.

These analysis (on all subjects and the three subsets) will also be repeated where subjects with a new or increased dosage of Class I/III AADs during the efficacy evaluation period will be categorized as not having achieved $\geq 90\%$ reduction. This will be performed on the ITT population. No imputation will be performed for missing data.

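### The 12-month plan does not separate primary success on a retained, previously failed anti-arrhythmic drug from success off drug, and tabulates no drug use by arm

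*Protocol*

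**What the plan says.** **Endpoint.** SAP 2.3.1 defines primary success as freedom from AF, flutter and atrial tachycardia "absent class I and III AADs except for a previously failed or intolerant class I or III AAD with no increase in dosage". Protocol 1.5.1 has the same exception. The matching failure criterion is "The use of a new or an increase in the dose of a previously failed class I or class III AAD", so an unchanged, previously failed drug is not a failure.

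**Who decides.** Attachment D has subjects in both arms prescribed a prior or failed AAD after the procedure. It calls for weaning at the 3-month visit, with an exception where the drug is medically indicated, or where a failed drug is kept at the same or a lower dose and "the attending physician recommends continuation of such medical management prophylactically". Protocol 1.3 describes the trial as open label.

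**Reporting.** SAP 8.6 says "Class I/III AADs will also be flagged in data listings, as well as presented in a separate listing", and then "No summaries of medications will be presented". Protocol 9.1 includes Class I and III AAD status among the items to be summarised by visit. SAP 13, which lists departures from the protocol, does not mention the difference.

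**Analyses.** The sensitivity analyses in SAP 9.3 are mITT, per-protocol, tipping point, geography and multiple imputation. The subgroups in SAP 6.3 do not include AAD status. AAD use splits only the AF-burden analyses (SAP 9.4.1, carried into 9.5.1, 9.5.6 and 9.5.7). One of the three subsets there is "Subjects who have taken any Class I/III AAD during the efficacy evaluation period".

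**The concern.** The rule is the same in both arms, but its use depends on a decision made after randomisation by someone who knows the assignment. Independent Holter review protects the reading of the rhythm. It does not protect the choice to keep a subject on drug. If one arm is kept on AADs more often and the drug suppresses arrhythmia, some of the difference in primary success belongs to the drug.

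A reader of the 12-month report would want to know how many subjects in each arm stayed on an AAD, how many primary successes were on drug, and whether the result holds off drug. For the primary endpoint the plan answers none of these. This matters because the trial is meant to support a premarket approval application.

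**Working it through.** **1. The plan's own sample size.** Inputs from Protocol 9.2 and SAP 4: 40% versus 65%, two-sided 0.05, 80% power, 2:1 allocation, 10% dropout. The pooled rate is (0.40 + 2 × 0.65)/3 = 0.5667.

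n(control) = [1.96 × √(0.5667 × 0.4333 × 1.5) + 0.8416 × √(0.40 × 0.60 + 0.65 × 0.35/2)]² / 0.25² = (1.1895 + 0.5006)²/0.0625 = 45.7, so 46 control and 92 treatment. Multiplying 46 by 1.10 gives 50.6, so 51:102 = 153, as stated. Exact power is 80% at 92:46 and 84% at 102:51.

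**2. Does any planned output give an off-drug result?**

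| Output | What it does with AADs |
|---|---|
| Primary analysis (SAP 9.1) | Fails new or increased AADs only |
| AF freedom (SAP 9.4.5) | Same rule |
| AF freedom regardless of AADs (SAP 9.4.6) | Ignores AADs |
| Burden endpoint defined as off all AADs (Protocol 1.5.2, SAP 2.3.2) | Tested in SAP 9.2 item 1 and 9.4.1 by failing new or increased AADs only |
| Burden subsets (SAP 9.4.1) | New or increased; not new or increased; any. None is off all AADs, and missing data are not imputed |
| Rhythm-treatment counts (SAP 9.5.5) | AAD therapy pooled with cardioversion and ablation, months 6 to 18 |
| Medication outputs (SAP 12) | Optional, after the 18-month visit |

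**3. How large could the effect be?** The documents give no continuation rate and no drug benefit, so every input here is an assumption. Assume no device effect, 40% off-drug success in both arms, and a drug that adds b to success among users. With use u in an arm, success is 0.40 + b × u. A false win is a two-sided p < 0.05 in favour of treatment at 102:51.

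Normal approximation: Φ{[(pT − pC) − 1.96 × SE0]/SE1}, with SE0 pooled and SE1 unpooled. For b = 0.30 and use of 60% versus 20%, pT = 0.58 and pC = 0.46. The pooled rate is 0.54, SE0 = 0.0855 and SE1 = 0.0852. Then (0.12 − 0.1676)/0.0852 = −0.56, which gives 29%. The exact binomial value is 28%.

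| AAD use, treatment vs control | b = 10 points | b = 20 points | b = 30 points |
|---|---|---|---|
| 20% vs 20% | 2.5% | 2.4% | 2.4% |
| 40% vs 20% | 4.2% | 6.4% | 9.8% |
| 60% vs 20% | 6.6% | 14.4% | 28.2% |

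Values are exact; the normal approximation is within one point of each.

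**4. What an off-drug sensitivity analysis could show.** Subtract assumed on-drug successes from 65% and 40%. Removing 5 points from each arm gives 60% versus 35% and 83% power at 102:51. Removing 15 and 5 points gives 50% versus 35% and 42%. Removing 20 and 5 gives 45% versus 35% and 22%. These are powers of the added analysis, not measures of bias in the primary one.

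**The case against.** Much of the opposing case stands.

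- Allowing a previously failed drug is an explicit endpoint choice, consistent between Protocol 1.5.1 and SAP 2.3.1 and applied to both arms. It is not itself an error.
- A reader might infer that a drug effect can never be told from a device effect here. The documents do not support that. AADs are recorded, flagged and listed by subject (SAP 8.6, Listing 16.2.7.11), and SAP 6.2 allows further analyses, so the question could be examined afterwards. The denominators of the any-AAD burden subset would also show use by arm, but only among subjects with burden data.
- Bias needs unequal continuation, which nothing in the documents shows. If the control arm were kept on drug more often, the bias would run against the convergent procedure.
- Protocol 9.1 can be read as naming the composite endpoint rather than promising a separate AAD table. SAP 8.6 still needs to be squared with it.
- Counting on-drug subjects as failures makes the unblinded physician's choice part of the outcome. It penalises the arm with more prophylactic prescribing, even for subjects who would have stayed free of arrhythmia without the drug. It is not a clean separation of effects.
- The exception may be narrower than it looks. Attachment D permits a lower dose of a failed drug, while SAP 7.4.4 and 7.4.5 treat any AAD that does not clearly match by name and dose level as new or increased.

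What remains is that none of this gives a pre-specified 12-month view of the primary endpoint by AAD status. A reconstruction from listings after unblinding would carry less weight.

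**Conclusion.** The concern holds in a limited form. No pre-specified 12-month analysis of the primary endpoint separates success on a retained AAD from success off all Class I/III AADs. No table of AAD use by arm is planned at that point, and SAP 8.6 sits against Protocol 9.1 without explanation. The one endpoint worded as off-drug is not tested as off-drug.

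The documents do not show that the primary comparison is biased. With equal use the false-win rate stays near 2.5%. The range of about 4% to 10%, and the extreme of about 28%, rest on assumed use and benefit and on no device effect. They show that the gap could matter, not that it does. This is an inexpensive improvement that should be made before unblinding, not a flaw in the endpoint.

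**What to change.** 1. Replace the SAP 8.6 sentence with a by-arm table of Class I/III AAD use at the 3-, 6- and 12-month visits: none; failed drug at the same dose; failed drug at a lower dose; new or increased. Split primary successes into on-AAD and off-AAD by arm. This also settles the conflict with Protocol 9.1; otherwise record it in SAP 13.
2. Add to SAP 9.3 a supportive analysis in the ITT population with the same test. Any Class I/III AAD use after a stated cut-off, through the 12-month visit, counts as failure. The cut-off must be a defined point after blanking ends, because weaning takes place at the 3-month visit and SAP 7.4.2 makes an in-window 3-month visit the last blanking day. State that the analysis rests on a post-randomisation choice and does not by itself separate drug from device effect. Given its power, read it by estimate and interval as well as p-value.
3. Make the SAP test of the burden endpoint (SAP 9.2 item 1 and 9.4.1) match its definition in SAP 2.3.2.
4. Reconcile Attachment D with SAP 7.4.4 and 7.4.5 on how a lower dose of a failed AAD is classified.

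The cost is SAP wording and two tables from data already collected. The primary endpoint and sample size do not change. The downside is a published off-drug success rate that will be lower than the primary rate wherever any success is on drug.
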